2.2.3. Pharmacokinetics

The concentrations of ALD403 will be measured in plasma from all ALD403-treated subjects using a validated assay. The PK analysis will include evaluations of concentration-time profiles for free ALD403 at the following times: pre-dose on Day 0, immediately post-dose (within 15 minutes of end of infusion) and Weeks 2, 4, 8, 12 (pre-dose), 24, and 32 or ET.

For subjects receiving placebo, selected plasma samples may be analysed for the potential presence of ALD403 using a validated assay.

If a subject terminates early from the clinical trial, all efforts will be made to collect blood samples to analyse for free ALD403 unless consent has been withdrawn.

2.2.4. Immunogenicity

Serum blood samples will be taken pre-dose on Day 0, and Weeks 2, 4, 8, 12 (pre-dose), 24, and 32 or ET to test for the development of antibodies to ALD403. The immunogenicity will be assessed in serum from all ALD403-treated subjects using a validated assay. Immunogenicity will not be assessed in placebo subjects.

For any samples that are positive for anti-ALD403 antibody, there may be additional testing to characterize the anti-ALD403 antibody for the potential to neutralize (NAb) ALD403 activity. Subjects who test positive for specific anti-ALD403 antibodies at the time of the last study visit will be asked to provide up to 2 additional blood samples for immunogenicity testing at 3 month intervals for up to 6 months. See the blinding plan for details concerning blinding and the capture of these samples.

2.3. Multiple Comparisons/Multiplicity

Multiplicity control will be used for the primary and key secondary endpoints. A combination of gate keeping and the Holm's procedure will be used to control the study wide Type-I error rate. At a high level this procedure will start with the 300 mg vs placebo comparison for the primary endpoint. If this is significant, testing will continue to the first group of key secondary endpoints for 300 mg where Holm's⁶ multiplicity procedure will be used. Testing will then continue to the second group of key secondary endpoints and then move on to the 100 mg group for the primary endpoint and subsequently the key secondary endpoints using the same methodology (Holm's within each group). Greater detail concerning this testing algorithm is provided below.

Confirmatory efficacy analysis will include testing, within the FAP, of eight endpoints (see below) across the two treatment arms:

- Change in frequency of migraine days (Weeks 1-12)
- 75% migraine responder rate (Weeks 1-4);
- 75% migraine responder rate (Weeks 1-12);
- 50% migraine responder rate (Weeks 1-12)
- Percentage of subjects with a migraine on the day after dosing
- Reduction in migraine prevalence from baseline to Week 4
- Headache Impact Test (HIT-6)
- Acute Migraine Medication Usage (Weeks 1-12)

A hybrid approach will be utilized to control for the experiment wise type-I error rate. The hybrid testing approach will be utilized a fixed sequence of tests and Holm's procedure as follows:

Compute p-value for Change in frequency of migraine days (Weeks 1-12) for the 300 mg dose group. If $p\text{-value} < 0.05$, declare statistical significance and go to step 2 below. Otherwise stop.

Compute p-values key secondary endpoints #1 and follow Holm's testing procedure, see [Table 2](#) for the P-value comparisons. If all endpoints are statistically significant, then go to step 3 below. Otherwise stop.

Compute p-values key secondary endpoints #2 and follow Holm's testing procedure, see [Table 2](#) for the P-value comparisons. If all endpoints are statistically significant, then go to step 4 below. Otherwise stop.

Compute p-value for Change in frequency of migraine days (Weeks 1-12) for the 100 mg dose group. If $p\text{-value} < 0.05$, declare statistical significance and go to step 5 below. Otherwise stop.

Compute p-values key secondary endpoints #3 and follow Holm's testing procedure, see [Table 2](#) for the P-value comparisons. If all endpoints are statistically significant, then go to step 6 below. Otherwise stop.

Compute p-values key secondary endpoints #4 and follow Holm's testing procedure, see [Table 2](#) for the P-value comparisons. If all endpoints are statistically significant, then go to step 7 below. Otherwise stop.

Compute p-values key secondary endpoints #5 and follow Holm's testing procedure, see [Table 2](#) for the P-value comparisons. If all endpoints are met statistically, then declare statistical significance. Otherwise stop.

All other efficacy analyses and associated p-values will be deemed exploratory and no adjustment for multiplicity will be used.

Table 2: Key Efficacy Analyses and Multiplicity Adjustment

Testing Sequence	Endpoint	Population	Declare Significant
Key Secondary #1	300 mg Wk1-4 75% responder rate	FAP	$p_{(1)} < 0.0167$
	300 mg Wk1-12 75% responder rate	FAP	$p_{(2)} < 0.025$
	300 mg % subjects with migraine on the day after dosing	FAP	$p_{(3)} < 0.05$
Key Secondary #2	300 mg migraine prevalence Day 1-28 Post dose	FAP	$p_{(1)} < 0.025$
	300 mg wk 1-12 50% responder rate	FAP	$p_{(2)} < 0.05$
Key Secondary #3	100 mg Wk1-4 75% responder rate	FAP	$p_{(1)} < 0.0167$
	100 mg Wk1-12 50% responder rate	FAP	$p_{(2)} < 0.025$
	100 mg % subjects with migraine on the day after dosing	FAP	$p_{(3)} < 0.05$
Key Secondary #4	100 mg migraine prevalence Day 1-28 Post dose	FAP	$p_{(1)} < 0.025$
	100 mg wk 1-12 75% responder rate	FAP	$p_{(2)} < 0.05$
Key Secondary #5	300 mg Acute medication usage	FAP	$p_{(1)} < 0.025$
	300 mg Change from baseline in HIT-6	FAP	$p_{(2)} < 0.05$

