2.5.2. Key Secondary Efficacy Analyses

Summary statistics including confidence intervals for the treatment differences will be used to summarize the results for the key secondary endpoints. Testing, as outlined below, will be used for the key secondary endpoints.

Responder Rates

Testing of the 75% migraine responder rate (Weeks 1-4), 75% migraine responder rate (Weeks 1-12) and 50% migraine responder rate (Weeks 1-12) endpoints will be performed with a CMH test controlling for the randomization stratification factors baseline migraine days (<17 days, \geq 17 days) and prophylactic medication use (use vs. no use). Cumulative distribution of the responder rate will be plotted.

Percentage of Subjects with a Migraine on the Day after Dosing

The percent of subjects with a migraine on the day after dosing key secondary endpoint will be tested with a stratified extended CMH test.⁴ Randomization stratification factors baseline migraine days (<17 days, \geq 17 days) and prophylactic medication use (use vs. no use) will be used for this test. An extended CMH test is used here as subjects with missing data will have a value imputed between 0 and 1 as outlined in Section 2.7.2.

Reduction in Migraine Prevalence from Baseline to Week 4

The reduction in migraine prevalence from baseline to Week 4 endpoint will be the difference in daily prevalence rates between Week 1 and baseline, Week 2 and baseline, etc. The treatment effect will be tested using a repeated-measures approach (Mallinckrodt and Lipkovich, 2016),⁵

using the subject level change in migraine rate (see Section 2.2.2) for Weeks 1, 2, 3 and 4 as the outcome variable. The model will specify an unstructured variance/covariance matrix and include the treatment group, week, baseline value of the outcome variable and with treatment group-by-week interaction. The Kenward-Roger approximation will be used to estimate the degrees of freedom.

Headache Impact Test (HIT-6)

The change in HIT-6 total score will be tested using an ANCOVA model similar to the one used for the primary endpoint. This model will include the HIT-6 change from baseline at Week 12 as the response variable. Treatment and the stratification factors will be the independent variables.

Acute Migraine Medication Usage

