The change in acute migraine medication usage between baseline and Weeks 1-12 will be tested using an ANCOVA model similar to the one used for the primary endpoint. This model will include the acute migraine medication usage change from baseline as the response variable. Treatment and the stratification factors will be the independent variables.

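### SAP 2.3 describes eight confirmatory endpoints for two doses, but Table 2 tests HIT-6 and acute medication usage for 300 mg only, so 100 mg has no controlled route to either

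*SAP*

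**What the plan says.** SAP 2.3 describes the testing plan at three levels.

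- **Scope sentence.** "Confirmatory efficacy analysis will include testing, within the FAP, of eight endpoints (see below) across the two treatment arms". The list below it includes HIT-6 and acute migraine medication usage (Weeks 1-12), with no dose limit.
- **Overview.** After the 300 mg families, testing will "then move on to the 100 mg group for the primary endpoint and subsequently the key secondary endpoints using the same methodology". SAP 2.2 counts HIT-6 and acute migraine medication usage among the key secondary endpoints.
- **Steps 1 to 7 with Table 2.** The 100 mg families are Key Secondary #3 and #4, and neither contains these two endpoints. They appear only in Key Secondary #5, as "300 mg Acute medication usage" and "300 mg Change from baseline in HIT-6". Step 7 is the last: "If all endpoints are met statistically, then declare statistical significance".

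The section then closes the sequence: "All other efficacy analyses and associated p-values will be deemed exploratory and no adjustment for multiplicity will be used".

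SAP 2.5.2 describes the two tests without naming a dose: "The change in HIT-6 total score will be tested using an ANCOVA model similar to the one used for the primary endpoint", and "The change in acute migraine medication usage between baseline and Weeks 1-12 will be tested". SAP 3.4.2.4 and 3.4.2.5 call for the p-values, again without a dose. SAP Section 4 records that both endpoints were moved up from the protocol's other secondary endpoints because they are in the testing algorithm. It does not add that this is true for one dose only.

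**The concern.** Read alone, the scope sentence and overview suggest that 100 mg is tested on all eight endpoints. Table 2 tests it on six. Two things follow.

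First, even if all seven steps succeed, 100 mg cannot make a type-I-error-controlled claim on HIT-6 or acute migraine medication usage, because the sequence ends at #5 and #5 holds only 300 mg tests.

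Second, the results tables may show 100 mg p-values for two endpoints that the SAP labels key secondary. Only Table 2 and the closing rule tell the reader that these are exploratory. If someone took them as confirmatory at 0.05 each, the joint error for that pair would be 1 - 0.95² = 0.0975 under independence, and at most 0.10. That would be an error of reporting and not a property of the tabulated procedure.

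**Working it through.** **1. Count of tests (SAP 2.3, steps 1 to 7 and Table 2).**

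| Dose | Primary | Families | Total |
|---|---|---|---|
| 300 mg | 1 | #1 (3), #2 (2), #5 (2) | 8 |
| 100 mg | 1 | #3 (3), #4 (2) | 6 |

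The total is 14. Eight endpoints for each of two doses would be 16. The two absent pairs are 100 mg HIT-6 and 100 mg acute migraine medication usage.

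**2. The plan's own figures.** Holm thresholds are 0.05/(m - k + 1) for the k-th smallest of m p-values. For m = 3 this gives 0.0167, 0.025 and 0.05; for m = 2 it gives 0.025 and 0.05. Table 2 reproduces. With 350 per group (SAP 1.5), the t-test for a 1-day difference with SD 4 has power 0.910, and the chi-squared test of 20% against 31% has power 0.918. Both agree with the stated 90%. These calculations cover the primary and 75% responder tests, 2 + 4 = 6 of the 14. The SAP gives no power for the other eight.

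**3. Error control with an added last family.** Let #6 hold the two missing 100 mg tests under Holm (0.025, 0.05), opened only if both #5 tests are significant. Take the first family in the sequence that contains a true null. A false claim in any later family requires every test in that family to be rejected, including the true null, so an error has already occurred there. The study-wide error is therefore at most the Holm error of that one family, which is at most 0.05. Simulation of the 16-test sequence (400,000 runs, within-dose correlation 0, 0.3 and 0.6) agrees:

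- global null: 0.0498 to 0.0502
- all 100 mg tests null: 0.0499 to 0.0505
- all four HIT-6 and medication tests null: 0.0450 to 0.0496
- only the added pair null: 0.0451 to 0.0493

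The Monte Carlo standard error is about 0.0003. Because #6 comes last, no decision among the first 14 tests can change.

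**4. What the added family would yield.** Assumptions, none of them from the documents: equal power for all 16 tests at two-sided 0.05; correlation r between endpoints within a dose; correlation between doses of 0.5 for the same endpoint and 0.5r otherwise. Results are shown as r = 0 / r = 0.6 (2,000,000 runs):

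| Power per test | #6 opens | At least one added claim | Both |
|---|---|---|---|
| 50% | 0.0003 / 0.057 | 0.0002 / 0.055 | 0.0001 / 0.051 |
| 80% | 0.062 / 0.311 | 0.059 / 0.307 | 0.046 / 0.292 |
| 90% | 0.262 / 0.526 | 0.258 / 0.523 | 0.223 / 0.506 |

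As a rough check, 14 independent tests all succeed with probability 0.9^14 = 0.229, 0.8^14 = 0.044 or 0.5^14 = 0.00006. Positive correlation raises these. The limit is reaching #6 rather than winning there: once it is open at 90% power, at least one claim follows with probability 0.98 to 0.99.

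If the first 14 tests have 90% power and the added pair only 50% or 80%, the chance of at least one claim is 0.175 / 0.385 or 0.245 / 0.506.

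**The case against.** The strongest reply is that the SAP does define the rule. Step 7 sends the reader to Table 2, Table 2 prints 300 mg on both #5 rows, and the next sentence makes everything else exploratory. The overview is offered only as a high-level account and does not mention #5 at all, so its reference to 100 mg key secondary endpoints can be read as #3 and #4. The absence of a dose in SAP 2.2 and 2.5.2 proves little, since those sections give no dose for the other endpoints either; dose is assigned only in 2.3. Table 2 also looks built by dose: the 50% and 75% Weeks 1-12 responder tests change places between the 300 mg and 100 mg families. Which extra claims to seek is the sponsor's choice.

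Most of this stands. A reader might infer that the SAP never reveals the restriction, that a row was dropped by mistake, or that error control fails. The documents support none of these. Table 2 shows the restriction, a deliberate design is plausible, and the sequence holds 5%. Nor is a protocol commitment broken: all five key secondary endpoints of Protocol 7.1.2 are tested for 100 mg in #3 and #4.

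The reply leaves two things open. The scope sentence and overview are still broader than the table, with no prose stating that the difference is intended. And ending the sequence at #5 gives up a controlled 100 mg test that would cost the other tests nothing.

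**Conclusion.** The concern holds as a minor point. The prose of SAP 2.3 is broader than Table 2, and 100 mg has no controlled route to two endpoints that the SAP itself calls key secondary. The operative rule is defined: the 100 mg tests of HIT-6 and acute migraine medication usage are exploratory by default.

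The gain from adding a route is modest and rests on assumed power and correlation. It is worth having near the 90% that the SAP claims for its primary and 75% responder tests, and negligible if power per test is nearer 50%. The argument for adding it is that it has no cost in alpha, subjects or earlier decisions, not that the gain is large.

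**What to change.** Before limited sponsor representatives are unblinded at Week 12 (SAP 1.4), extend the sequence:

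- In step 7, keep the declaration of significance and add that testing goes on to step 8 if both #5 tests are significant.
- Add step 8 and Key Secondary #6 to Table 2: 100 mg acute migraine medication usage (Weeks 1-12) and 100 mg change from baseline in HIT-6 at Week 12, in the FAP, by Holm with p(1) < 0.025 and p(2) < 0.05.

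The cost is one amended sentence, one new step and two table rows. No data are added, no earlier threshold or decision changes, and the study-wide 5% is kept. A step written after unblinding would not be credible as prespecified.

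If the sponsor intends the restriction, reword the scope sentence and overview in SAP 2.3 to match Table 2: six endpoints for both doses, with HIT-6 and acute migraine medication usage confirmatory for 300 mg only. A clause in SAP 2.2 and Section 4 could say the same and note that the 100 mg p-values are exploratory. This alternative is clarification only and changes no test.

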2.2. Clinical Trial Endpoints

The efficacy, safety, pharmacokinetic and immunogenicity of ALD403 will be assessed using the following endpoints. Greater detail concerning these endpoints can be found in Section [2.2.2](#).

Primary Efficacy Endpoint

- Change in frequency of migraine days (Weeks 1-12)

Key Secondary Efficacy Endpoints

- 75% migraine responder rate (Weeks 1-4)
- 75% migraine responder rate (Weeks 1-12)
- 50% migraine responder rate (Weeks 1-12)
- Percentage of subjects with a migraine on the day after dosing
- Reduction in migraine prevalence from baseline to Week 4
- Headache Impact Test (HIT-6)
- Acute Migraine Medication Usage

Other Secondary Efficacy Endpoints

- Headaches/migraines with acute medication usage
- Change in frequency of migraine days (Weeks 1-24)
- 100% migraine responder rate (Weeks 1-12)
- Migraine responder rates for time periods other than Weeks 1-12

- Change in frequency of migraine days between baseline and time periods other than Weeks 1-12
- Headache responder rates
- Change in the frequency of headache days
- Percent change in headache or migraine days
- Time to first migraine after dosing
- Headache/migraine hours
- Headache/migraines with severe intensity
- Patient Global Impression of Change (PGIC)
- Short-Form Health Survey (SF-36 v 2.0)
- Health-Related Quality of Life (EQ-5D-5L)

Tertiary Endpoints

- Headache episodes/migraine attacks
- Migraine symptom-free days
- Most Bothersome Symptom (MBS)
- Migraine Free Days

Safety Endpoints

- Adverse events (AEs) and serious adverse events (SAEs)
- Clinical laboratory assessments
- Vital signs
- Electrocardiograms (ECGs)
- Columbia-Suicide Severity Rating Scale (C-SSRS)

Pharmacokinetic Endpoints

- Free ALD403 plasma concentrations

Immunogenicity Endpoints

- Development of specific anti-ALD403 antibodies
- Characterization of specific anti-ALD403 antibodies for neutralizing activity

2.2.1. eDiary

Subjects will complete a daily headache eDiary from the time of screening to Week 24. The diary includes two separate functionalities. The evening report is completed each trial day whether or not the subject had a headache. Among other items this evening report is where

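### SAP Section 2.3, step 7 calls for Holm on two 300 mg endpoints, then words the declaration as both-or-none

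*SAP*

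**What the plan says.** SAP Section 2.3 sets out a seven-step chain. Steps 1 and 4 are single tests of the primary endpoint at 300 mg and 100 mg. Steps 2, 3, 5, 6 and 7 each test a group of key secondary endpoints by Holm, with ordered thresholds in the column of Table 2 that states when a result is declared significant.

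Step 7 opens: "Compute p-values key secondary endpoints #5 and follow Holm's testing procedure". Its group, Key Secondary #5, has two rows in Table 2: acute medication usage at 300 mg, and "300 mg Change from baseline in HIT-6". Their thresholds are p(1) < 0.025 and p(2) < 0.05. Step 7 then ends: "If all endpoints are met statistically, then declare statistical significance. Otherwise stop".

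The earlier Holm steps use the condition differently. Step 6, for example, says: "If all endpoints are statistically significant, then go to step 7 below". The overview paragraph of the section describes the within-group rule as "using the same methodology (Holm's within each group".

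On scope, Section 2.3 says: "Confirmatory efficacy analysis will include testing, within the FAP, of eight endpoints (see below) across the two treatment arms". The list that follows includes HIT-6 and acute migraine medication usage. The paragraph just before Table 2 adds: "All other efficacy analyses and associated p-values will be deemed exploratory".

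**The concern.** In steps 2, 3, 5 and 6, success on every endpoint in the group only opens the next step. Which endpoints are declared within the group is left to Holm and Table 2. Step 7 has no next step, so the same condition falls on the declaration itself. The step therefore holds two rules: Holm, which can declare one endpoint alone, and a both-or-none rule.

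At stake is one 300 mg claim, for whichever of the two endpoints has the smaller p-value, when the other one fails. If the wording is settled only after results are known, the choice of reading decides whether the claim stands and could look result-driven.

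A lesser point is that the scope sentence can be read as promising every listed endpoint at both doses, while the chain tests HIT-6 and acute migraine medication usage at 300 mg only.

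**Working it through.** **1. The plan's own thresholds.** Holm compares the j-th smallest of m p-values with 0.05/(m − j + 1).
- m = 3: 0.05/3 = 0.0167, 0.05/2 = 0.025, 0.05/1 = 0.05.
- m = 2: 0.05/2 = 0.025, 0.05/1 = 0.05.

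These match Table 2 exactly, including Key Secondary #5.

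**2. Where the two rules differ.** Let p(1) ≤ p(2) be the two step 7 p-values, and take an endpoint as met when it passes its Holm threshold.

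| p(1) | p(2) | Holm and Table 2 | Closing sentence |
|---|---|---|---|
| ≥ 0.025 | any | none | none |
| < 0.025 | < 0.05 | both | both |
| < 0.025 | ≥ 0.05 | smaller only | none |

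Only the last row differs. Example: 0.010 < 0.025 but 0.060 ≥ 0.05, so Holm declares one endpoint and the closing sentence declares none.

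**3. Type I error in step 7**, with both nulls true and all earlier gates open. For independent tests:
- Holm, at least one false claim: 1 − (1 − 0.025)² = 0.0494.
- Both-or-none: 0.05² − (0.05 − 0.025)² = 0.0025 − 0.000625 = 0.0019.

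Over correlations 0 to 0.6, Holm gives 4.5% to 4.9% and the closing sentence 0.2% to 1.0%. With one null true and the other endpoint at an assumed 90% power, the chance of falsely declaring the null endpoint is 4.2% to 4.6% under Holm and 3.4% to 4.4% under the closing sentence. Nothing exceeds 5%.

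**4. Power.** The documents give no effect size for either endpoint. SAP Section 1.5 covers only the primary endpoint and the 75% responder rates. The figures below therefore rest on assumptions: 14 normal statistics with one common correlation of 0.3, 0.5 or 0.7; the stronger step 7 endpoint at 90% power; all 12 earlier tests at 90% or 80% power; Holm within groups; and gates that open only if the whole group passes (1,000,000 draws per scenario). The loss is the fall in the probability of declaring the stronger endpoint, in percentage points over all trials, when the closing sentence replaces Holm.

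| Power of the other endpoint | Loss, earlier tests at 90% | Loss, earlier tests at 80% |
|---|---|---|
| 90% | 0.6 to 1.5 | 0.1 to 0.5 |
| 80% | 2.9 to 3.9 | 0.8 to 1.3 |
| 60% | 10.4 to 12.2 | 4.0 to 4.9 |

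Step 7 is reached in 46% to 66% of trials with earlier tests at 90% power, and in 23% to 47% at 80%.

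**5. Count of tests.** Steps 1 to 7 hold 1 + 3 + 2 + 1 + 3 + 2 + 2 = 14 tests, of which 12 come before step 7. That is six endpoints at both doses (12) plus two endpoints at 300 mg only (2). Eight endpoints at two doses would be 8 × 2 = 16, a number that the SAP does not print.

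**The case against.** The strongest reply is that the SAP largely settles step 7 itself. The step orders Holm with Table 2 before it reaches the closing sentence. The Table 2 column states when each result is declared. Steps 2, 3, 5 and 6 contain no declaration wording of their own, so declarations there must come from the table too. A both-or-none rule would also not need the 0.025 threshold, since requiring both p-values below 0.05 already controls the error. On this view the last sentence is a loose ending to a chain that has no step 8. This stands as evidence of intent, and for that reason a reader should not infer that the sponsor chose a both-or-none rule. It does not remove the contradiction, because the closing sentence is equally part of the written decision rule.

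The objection to the power figures also stands. They depend on assumed powers and a single common correlation, and they apply only if the closing sentence is followed over Table 2. They show a range and do not establish a size.

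On scope, a reader might infer that the plan promises 16 confirmatory tests and leaves two out, or that the 100 mg status of HIT-6 and acute migraine medication usage is undefined. The documents do not support either. The scope sentence can be read as eight endpoints used over the two arms together. Table 2 prints 300 mg on both rows of Key Secondary #5, and the paragraph before the table makes every other efficacy test exploratory. Section 2.2 lists both endpoints under "Key Secondary Efficacy Endpoints" without a dose, but dose allocation belongs in Section 2.3.

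**Conclusion.** The contradiction in step 7 is real but minor. As written, the same pair of p-values can yield one 300 mg claim or none, and only when p(1) < 0.025 and p(2) ≥ 0.05. Holm was very likely intended, so the closing sentence is the text to correct.

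Type I error is not inflated under either reading, because the closing sentence is only conservative. The primary comparisons and the other ten earlier tests are untouched. The power at stake for the stronger endpoint cannot be fixed from the documents. About 0.1 to 12 points covers the scenarios tried, and the upper end needs a companion endpoint at 60% power together with 90% power in every earlier test.

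The scope sentence is imprecise, and aligning it is editorial: no result changes, because the 100 mg tests of the two endpoints are already exploratory.

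**What to change.** Make the change before the unblinding that SAP Section 1.4 sets for when the last subject has completed the Week 12 visit. Replace the closing sentence of step 7 with:

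> Declare each endpoint by the Holm thresholds in Table 2: the smaller p-value if < 0.025 and, if so, the larger if < 0.05. Otherwise stop.

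In the same revision, align the scope sentence with the chain, for example by stating 14 tests in the FAP: six endpoints at both doses, plus HIT-6 and acute migraine medication usage at 300 mg only.

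The cost is one sentence in step 7 and, as an editorial addition, one in the scope statement. No threshold changes, no test loses power, and the overall 5% level is kept.

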1.5. Sample Size

The planned sample size for this study is 1050 randomized and treated subjects. These subjects will be allocated into 3 treatment groups in a 1:1:1 ratio. Pair-wise testing of each ALD403 group vs. placebo will be performed. Three hundred and fifty subjects per group provides at least 90% power for the primary endpoint for each comparison assuming a treatment effect of at least 1 day and a common standard deviation of 4 days or less. For the key secondary 75% responder rate endpoints 90% power is achieved for the pair-wise comparisons, assuming a placebo responder rate of 20%, and an ALD403 rate of 31%. These sample size calculations have been performed using Pass 2008 and are based upon a t-test and chi-squared test that should approximate the ANCOVA and CMH tests.³

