2.5. Statistical Assessment of the Trial Objectives

2.5.1. Primary Endpoint

Hypothesis testing will be performed for the primary endpoint: change in frequency of migraine days (Weeks 1-12). This endpoint will be calculated as outlined in Section 2.2.2 and will utilize the missing data rules provided in Section 2.7.2. Summary statistics including confidence intervals for the treatment differences will be used to summarize the results for the primary endpoint. Testing will also be employed. The hypotheses tested are

$$H_0: \Delta_{\text{plb}} = \Delta_{403} \qquad H_a: \Delta_{\text{plb}} \neq \Delta_{403}$$

where Δ_{403} is the change in migraine days for subjects in the ALD403 treatment arm and Δ_{plb} is similarly defined for the placebo subjects. The change from baseline is expected to be negative as migraines are being reduced. While the test outlined above is two sided, as is the alpha level used for this study (i.e. 5%), clinically relevant results require a larger reduction of migraines on the ALD403 arms.

An ANCOVA model will be used to test for a difference between treatment arms. This model will include the change from baseline measure as the response variable. Treatment and variables measuring the stratification factors concepts: baseline migraine days (continuous covariate) and prophylactic medication use (binary covariate: use vs. no use) will be the independent variables.

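### The confirmatory migraine-prevalence model leaves out prophylactic medication use, a randomisation stratum that every other confirmatory analysis includes; its contrast and day limits should be settled in the same edit

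*SAP*

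**What the plan says.** **Model.** SAP 2.5.2 tests the reduction in migraine prevalence with a repeated-measures model on the four weekly changes. The model is to "include the treatment group, week, baseline value of the outcome variable and with treatment group-by-week interaction". Protocol 13.4.2 lists the same terms, with visit in place of week. Neither has a term for prophylactic medication use.

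**Stratification.** SAP 1.3 and protocol 8.3.2 stratify randomisation by screening migraine days (below 17, or 17 and above) and by prophylactic medication use.

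**Testing order.** SAP 2.3 pairs this endpoint, labelled "300 mg migraine prevalence Day 1-28 Post dose" in Table 2, with the 300 mg 50% responder rate in Key Secondary #2. The rule for leaving that step is "If all endpoints are statistically significant, then go to step 4 below. Otherwise stop", and step 4 is the 100 mg primary endpoint. The same prevalence test appears for 100 mg in Key Secondary #4.

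**Days.** Table 4 sets Weeks 1-4 at Days 0-27, where Day 0 is the first day of treatment. SAP 3.4.2.1 identifies the day after dosing as Day 1.

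**The concern.** A factor used to stratify randomisation is normally carried into the analysis. Stratification balances the factor across arms, which reduces the true variance of the treatment difference. A model without the factor still counts its contribution as residual noise. The standard error is then too large, and the test rejects less often than it should, under the null and under the alternative.

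Here the omission falls in a test with consequences beyond its own endpoint. If the 300 mg prevalence test fails, confirmatory testing stops before the 100 mg primary endpoint. If the 100 mg version fails, testing stops before the 300 mg acute medication and HIT-6 claims in Key Secondary #5. Avoidable loss of precision is undesirable at such a point.

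Two smaller matters affect the same test. SAP 2.5.2 does not say in so many words which contrast from the treatment-by-week model supplies the p-value. The day range in Table 2 also differs from the one in Table 4.

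**Working it through.** **1. The plan's own power figures.** SAP 1.5 states "Three hundred and fifty subjects per group provides at least 90% power for the primary endpoint for each comparison". The inputs given there are a difference of 1 day and an SD of 4 days. With 350 per group and two-sided 5%, the non-centrality is 1 / (4 × √(2/350)) = 3.307, and power is Φ(3.307 − 1.96) = 0.911. For the 75% responder rate, 20% against 31% gives 0.918. Both stated figures reproduce. The documents give no effect size or power for the prevalence endpoint, so steps 3 and 4 rest on assumptions.

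**2. Where prophylactic use appears in the confirmatory analyses**

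| Endpoint | Method | Prophylactic use included? |
|---|---|---|
| Migraine days, Weeks 1-12 | ANCOVA (SAP 2.5.1) | Yes |
| 75% and 50% responder rates | CMH (2.5.2) | Yes |
| Migraine on day after dosing | Extended CMH (2.5.2) | Yes |
| HIT-6, Week 12 | ANCOVA (2.5.2) | Yes, as a stratification factor |
| Acute migraine medication | ANCOVA (2.5.2) | Yes, as a stratification factor |
| Migraine prevalence | Repeated measures (2.5.2) | **No** |

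The migraine-day stratum is not missing from the last row, because the baseline value carries it in continuous form.

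**3. Cost of the omission, by formula.** Let R² be the share of residual variance explained by prophylactic use, with the factor balanced across arms. Leaving it out inflates the estimated standard error by 1/√(1 − R²) while the true one is unchanged. The effective critical value becomes 1.96/√(1 − R²). Then type I error = 2 × [1 − Φ(1.96/√(1 − R²))] and power = Φ(δ − 1.96/√(1 − R²)). Assume an effect of 0.245 residual SD with 350 per arm: δ = 0.245/√(2/350) = 3.241, so power with the factor included is Φ(1.281) = 0.900.

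| R² (assumed) | Effective critical value | Type I error, omitted | Power, omitted | Power, included |
|---|---|---|---|---|
| 0.010 | 1.970 | 0.049 | 0.898 | 0.900 |
| 0.058 | 2.020 | 0.043 | 0.889 | 0.900 |
| 0.198 | 2.189 | 0.029 | 0.854 | 0.900 |

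**4. Check by simulation.** Single-outcome ANCOVA, 700 subjects, assumed 45% prophylactic use, 3,000 runs. For the same three R² values, type I error was 0.043, 0.042 and 0.027 with the factor omitted, against 0.045, 0.050 and 0.052 with it included. Power was 0.90, 0.88 and 0.86 omitted, against 0.90, 0.89 and 0.90 included. The simulation standard error is about 0.004 for type I error and 0.005 for power, so this agrees with step 3.

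**5. Place in the sequence.** Six 300 mg tests precede the 100 mg primary test: the primary endpoint, three in Key Secondary #1 and two in #2. In #2 the smaller p-value must be below 0.025 and the larger below 0.05, so a prevalence p-value of 0.05 or more always stops the sequence there.

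**6. Day windows.** Days 0-27 and Days 1-28 share 27 of 28 days; only Day 0 and Day 28 differ. If each window is cut into consecutive sevens, each week shares 6 of 7 days (Week 1: Days 0-6 or 1-7; Week 4: Days 21-27 or 22-28). No section gives the limits of the individual weeks.

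**The case against.** The strongest reply is that the protocol and SAP prespecify the same model, so the documents do not conflict and no error rate is at risk. That stands. The omission is a missed improvement and does not invalidate the test. It also stands that the loss is trivial if prophylactic use predicts little of the weekly change once baseline is in the model.

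A reader might infer more from the unnamed contrast: that several equally valid p-values are open after unblinding. For example, if the four-week average has 90% power (non-centrality 3.24), the weekly effects are equal and the between-week correlation is 0.4 to 0.7, the Week 4 contrast has non-centrality 3.24 × √((1 + 3ρ)/4), which gives 67% to 81% power at two-sided 5%. The arithmetic is right, but the documents do not support treating the two readings as equal. Protocol 12.1.2 describes an average rate over Weeks 1, 2, 3 and 4, SAP 2.5.2 takes all four weeks as the outcome, and the Table 2 label spans 28 days. Only the endpoint name suggests Week 4 alone. The 90% starting power and equal weekly effects are assumed, and an effect growing over the weeks could reverse the ordering. What remains is one clarifying sentence.

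A reader might also infer that this one test decides whether 100 mg is tested at all. It is one of six tests that must succeed, and a stop removes only confirmatory status: under SAP 2.3 other efficacy analyses are still reported as exploratory.

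**Conclusion.** The point holds as a modest improvement. The prevalence model is the only confirmatory analysis that ignores prophylactic use, and no reason is given. The test keeps its type I error at or below 5% but is somewhat conservative. The loss of power runs from negligible (factor explaining 1% of residual variance) through about 1 point (6%) to between 4 and 5 points (20%). These figures assume 90% power with the factor included, balanced arms and a single outcome in place of four weekly ones. The documents supply no value for the share of variance explained.

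The contrast and the day windows are clarifications. The average over Weeks 1-4 is already the better supported reading, and the window mismatch moves one day at each end.

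**What to change.** In SAP 2.5.2, for the prevalence endpoint:

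- Add prophylactic medication use to the repeated-measures model, using the as-randomised value. This matches the rule SAP 3.4.2 sets for the CMH tests.
- State that the p-value is for the treatment difference averaged with equal weight over Weeks 1, 2, 3 and 4.
- Give one set of day limits for each of the four weeks, and make Table 2 and Table 4 agree with it.
- Record the added covariate in SAP section 4, because the model is also written in protocol 13.4.2.

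The edit applies to both doses. It changes no data collection, sample size or Holm threshold. Its only cost is a documented departure from the protocol model, and it should be made before the unblinding that SAP 1.4 places after the last subject's Week 12 visit.
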